### **10.5 Participant population**

Participants will be adult cataract patients of any sex, aged 50 years or above with astigmatism >1.0D who have already consented for bilateral cataract correction surgery at the REI of Derriford Hospital.

### **10.6 Procedure(s) to account for missing or spurious data**

If the participants miss the study visit appointment without notification, they will be contacted for two more attempts within two months of the planned visit date. A letter of notification will be sent to their home address and if they have not replied within four weeks, they will be withdrawn from the study and any related data will be discarded.

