### **3.5 Secondary endpoints/outcomes**

1. The eye tracking characteristics (gaze duration, area of interest by gaze pattern and its percentage duration gaze time).

Vision and balance changes after bilateral implantation of Toric IOLs  
IRAS ID: 286913

2. IOL rotation by measuring degrees of rotation from intended position and degrees rotation from steepest meridian with digital slit lamp and IOL tilt and decentration using Pentacam4. This will be part of the routine eye assessment for post cataract surgery with Toric IOL.
3. Visual acuity which is also part of routine eye assessment for all post cataract surgery patients.
4. Fear of falling and fall efficacy scale via questionnaire.
5. Cataract specific quality of life questionnaire (CAT-PROM 5)

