### **7.6 Baseline data**

At each study visit based at the UoP, the participant's full name, DOB, address and contact details will be checked for identification purposes. These details will remain separate from the study data which will be identified using the unique study number allocated to the participants.

The outcome measures will include the following:

- General demographic information such as age, gender, ethnicity, relevant medical history, cataract diagnosis and vision assessment results. This will last about 10 minutes.
- Dynamic stability assessment lasts about 30 minutes. Three motion sensors will be put on the participants' body (neck, lower back and upper leg) and they will be asked to wear a special eye tracking glass (figure 1). After that, the participants will be asked to perform a Timed Up and Go (TUG) test which involves getting up from a chair, walking 3m-distance and return to sit back on the chair. They will also be asked to walk over obstacles on level ground and the last mobility task is walking up and down a standardized staircase. Movement outcomes will be measured using three-dimensional motion analysis

Vision and balance changes after bilateral implantation of Toric IOLs  
IRAS ID: 286913

(ProMove 3D, Inertia Technology, The Netherlands) and eye tracking data will be collected *via* Tobii-pro glasses 2 (Tobii AB, Sweden) (figure 2 and 3). Three trials will be taken to estimate the average and the best recorded time will be taken for the TUG test. As all the participants are active community dwelling elderly without mobility problem, the dynamic stability tasks are no more demanding than their usual daily activities. The PPI also include discussion about the demand of the assessment and all participants agreed the dynamic stability tests only required low level mobility and no concerns were raised.

- Some qualitative data will be collected *via* self-administered questionnaires which takes about 15 minutes. Risk of fall will be assessed with the short Fall Efficacy Scale (FES-short) and Fear of Falling questionnaire. Vision specific quality of life will be assessed with CAT-PROM 5 questionnaire.

- Standard visual function assessment will also be carried out to assess visual acuity and degree of astigmatism and this takes about 20 minutes.

A paper CRF has been prepared for this study to collect data directly relevant to the objectives and outcomes measures detailed in the protocol.

[figure not shown]
[figure not shown]

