## 7.8 Long term follow-up assessments/ lost to follow-up

There is no long term follow up assessments. If the participants miss their scheduled study visit, they will be contacted by telephone or email (depending on their indicated preference). If no response, two more attempts within 2 months will be made. Participants who are not contactable will be marked as lost to follow-up and notification sent to their GP and the PI for their medical records. A notification letter will be sent to the participants' address or email account.

Vision and balance changes after bilateral implantation of Toric IOLs  
 IRAS ID: 286913

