## **8.6 Cataract schedules**

Each eye will be implanted with one IOL in the capsular bag and two separate occasions. PI reported at the time of writing this protocol, the second eye cataract surgery would be scheduled at around four months after the first eye surgery.

Orientation of the IOLs will be checked before and after implantation of IOLs by the ophthalmologists as part of routine care. The PI has extensive experience using Toric IOLs for cataract surgery, they communicated that the cataract surgery using Toric IOLs usually took five to eight more minutes because it took longer time to put in and to ensure the axis of the lenses were in a precise position for correction of astigmatism.

Vision and balance changes after bilateral implantation of Toric IOLs  
 IRAS ID: 286913

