### 10.3.2 Primary outcome analysis- Dynamic stability in three functional activities

The following outcomes will be collected at three time points: before surgery, 3 to 6 months after first and second eye surgery.

Outcome measures	Data collected	Data type/ details	Quantitative Statistical Analysis
Dynamic stability during turning, obstacle crossing and stair walking	Accelerometers data (angular position and acceleration) of change in head tilting and centre of mass will be recorded  Performance of TU&G test	Interval  Centre of mass and head movement will be calculated using ProMove 3D (Inertia Technology, The Netherlands) and MATLAB.  The angular position, velocity and acceleration of the sensors will be tracked on each participant  Duration in seconds of TU&G test	The average reading of the 3 trials in each functional activity will be calculated.  Mixed ANOVA and post-hoc Bonferroni tests will be used to determine the differences between the Toric IOLs group and Monofocal IOLs group before surgery and 6 months after second eye surgery.

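### Section 10.6 withdraws a participant after one unanswered missed visit, with no route back to visit 3, where the lens comparison is made

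*Combined protocol and SAP*

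**What the plan says.** Section 10.6 sets the trigger: "If the participants miss the study visit appointment without notification, they will be contacted for two more attempts within two months of the planned visit". Next comes a letter; "if they have not replied within four weeks, they will be withdrawn from the study". The same sentence also has that participant's data thrown away. The rule names no particular visit and exempts none.

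Section 7.8 covers the same situation with a milder consequence: "Participants who are not contactable will be marked as lost to follow-up". The GP and the PI are told and the participant is sent a notification. Section 7.8 withdraws nobody and sets no deadline for a reply, but it does not provide for an invitation to a later visit either. Section 7.10 defines the end of the trial by the last visits of everyone who has not withdrawn, so a withdrawn participant is not expected at visit 3.

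The primary analysis table (10.3.2) states the lens comparison as "before surgery and 6 months after second eye surgery", and the secondary table (10.3.3) repeats it. Visit 3 is the only study visit after the second operation (7.7). Section 8.6 reports that "the second eye cataract surgery would be scheduled at around four months after the first eye surgery". Section 7.6 describes the falls and CAT-PROM5 forms as "self-administered questionnaires which takes about 15 minutes", although they are scheduled at the campus visits.

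**The concern.** Missing one visit and leaving the study are different events, and 10.6 treats the first as the second once a letter goes unanswered. For visit 3 this matters little, because nothing comes after it. For visit 2 it matters a good deal: the stated comparison uses baseline and visit 3, so a participant who missed only visit 2 could still supply everything that comparison needs. The rule closes that participant instead.

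These people are not necessarily out of reach. They remain on the surgical list for the second eye, the PI's team at the same hospital operates on them (section 5), and 7.8 already tells the PI about them. Section 7.2 gives every participant the right to withdraw, but not answering a letter is not a use of that right.

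At stake are avoidable missing outcomes and, if silence is related to how the person is doing, a visit 3 sample tilted towards those who are easiest to follow. The questionnaires, which could be completed at home, are lost by the same rule.

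**Working it through.** **1. The plan's own sample size.** Inputs from 10.1: effect size f = 0.25, alpha 0.05, power 85%, mixed ANOVA with lens as the between factor. The number of measurements m and their correlation rho are not given. The between-factor test has noncentrality f² × N × m / (1 + (m − 1) × rho) with 1 and N − 2 degrees of freedom. With m = 2 and an assumed rho of 0.5, N = 110 gives 0.0625 × 110 × 2 / 1.5 = 9.17 and power 85.1%. This is the stated 55 per group. Inflation gives 55 / 0.8 = 68.75, so 69 per group against the planned 70.

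The match fits a two-measurement comparison but does not prove one was used. With m = 3 the required N is 98 at rho 0.5 and 118 at rho 0.7, so a correlation in between would also give about 110.

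**2. Order of events, in months after first-eye surgery.** Visit 2 is due at months 3 to 6 (7.7). With the second operation at about month 4, the visit 3 window is 4 + 3 = 7 to 4 + 6 = 10. Suppose the letter goes out only when the full two months have passed. Withdrawal is then complete at the visit 2 date plus 2 months plus 28 / 30.4 = 0.92 months.

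| Visit 2 due | Withdrawal complete by | Against the month 7–10 window |
|---|---|---|
| Month 3 | 3 + 2 + 0.92 = 5.9 | before it opens |
| Month 4 | 4 + 2 + 0.92 = 6.9 | just before it opens |
| Month 6 | 6 + 2 + 0.92 = 8.9 | inside it |

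On this slowest timetable, withdrawal precedes the window when visit 2 was due by about month 7 − 2.92 = 4.1. That covers a visit 2 held before the second operation, which is when it would reflect one operated eye. Quicker contact attempts, or a later second operation, make withdrawal before the window more likely. Even in the last row, withdrawal is complete before the window closes at month 10.

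**3. Outcomes removed.** The documents give no rate of silent misses, so both rates here are assumptions. Outcomes lost = 140 × (share missing visit 2 without reply) × (share of those who would have attended visit 3 if asked).

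- Low: 140 × 0.05 × 0.30 = 2.1
- Middle: 140 × 0.10 × 0.50 = 7.0
- High: 140 × 0.15 × 0.70 = 14.7

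The planned margin is 140 − 110 = 30.

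**4. Power (m = 2, rho = 0.5).** At exactly 20% loss, 112 remain and power is 85.7%. If all these losses sit inside the 20%, planned power is kept. If they come on top of it:

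- Low: 112 − 2.1 = 109.9, in effect 110, power 85.1%
- Middle: 112 − 7 = 105, power 83.4%
- High: 112 − 14.7 = 97.3, slightly under the 98 that gives 80.8%

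**The case against.** **The rule is not hair-trigger.** It needs a miss without notice, failed contact attempts and four weeks of silence after a letter. Anyone who replies stays in. That is right, and the point concerns only those who do not reply.

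**Section 7.8 is gentler.** A reader might infer that both sections withdraw the participant. Only 10.6 does; 7.8 marks loss to follow-up and notifies the PI, so a channel to the hospital exists. What stands is that neither section uses that channel to offer visit 3, and the two do not agree.

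**Three time points.** Sections 3.6 and 10.3.2 collect the primary outcome three times. A three-level mixed ANOVA on complete cases would drop anyone without visit 2, whatever the follow-up rule. That is a fair limit: the argument relies on the comparison as 10.3.2 and 10.3.3 state it, and on the pre- versus post-surgery factor in 10.3.

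**No evidence on frequency or direction.** It is tempting to say that visit 2 is the visit most often missed because its window straddles the second operation. The documents give no miss rate by visit, the window leaves room to rebook on either side of surgery, and 13.3 reports few dropouts in the team's earlier lens trials. That silence is related to outcome is also plausible rather than shown.

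**Power.** A reader might conclude that the trial becomes underpowered. Nothing in the documents indicates that these losses would come on top of the 20% allowance.

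**Acuity from routine records.** Section 3.5 says "Visual acuity which is also part of routine eye assessment for all post cataract surgery patients", which suggests an easy substitute for a missed visit. It is not one. The surgical team knows the lens (7.4), the routine follow-ups in Appendix 1 are undated, and 10.3.3 needs unaided and aided acuity in LogMAR.

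**Re-approaching silent people.** Section 7.2 rules out undue influence, so an approach through the treating team needs ethics approval. That adds to the cost but does not defeat the change.

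**Conclusion.** The point holds. Followed as written, 10.6 ends study follow-up for a participant who silently misses only visit 2, although the stated lens comparison does not use visit 2 and visit 3 may still be obtainable. The result is avoidable loss that may be related to outcome. Adverse events already open continue to be followed after withdrawal (9.3, 9.4), so what is lost is outcome data.

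The size is uncertain: about 2 to 15 of 140 outcomes, with 7 in the middle, on assumed rates. The top of the range needs both rates at their extreme. Planned power is at risk only if total loss exceeds the 20% allowance. The documents do not support saying that withdrawal always precedes visit 3, that visit 2 is the most missed visit, or that the sample size is wrong.

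The discarding of data already held, which contradicts 7.2, is a separate defect. Correcting it would not bring anyone back to visit 3. This is a change that should be made, since it is specific and cheap.

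**What to change.** Replace the withdrawal sentence in 10.6 and align 7.8 with it:

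> A missed visit is recorded as missed. The participant stays in the study and is invited to every later visit unless they ask to stop. After a missed visit 2, the visit 3 invitation is sent again after second-eye surgery, through the PI's team if needed. Lost to follow-up is assigned only after the visit 3 window closes.

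Add to 7.7 or 10.6:

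> If a visit cannot be attended, the self-administered questionnaires may be posted or emailed, with the mode and date of completion recorded.

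Do not use acuity from routine records in the main analysis, because it may be unmasked, taken at another time and on another scale. At most, use it in a flagged sensitivity analysis.

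The cost is protocol and consent wording, ethics approval of the re-invitation, postage, and a few questionnaires completed by a different mode. No visit is added.

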### 7.2 Consent

Prior to participant recruitment and any procedures for this study, ethical approval will have been obtained from both the Health Research Authority and the NHS Research Ethics Committee.

Potential participants will be asked to sign the written informed consent form on the same day as their pre-surgical routine visit at the REI (where they are consented for surgery) by a member of the research team. This is to accommodate the cataract surgery clinical pathway and to reduce the need for the patients to travel back to REI for signing the written informed consent form. Following the current cataract surgery clinical pathway, patients attend the REI for a pre-assessment cataract clinic appointment to discuss cataract surgery with their ophthalmology surgeons. If the patients would like to go ahead, consent for surgery is obtained during this appointment. The patients are then placed on a waiting list and the next time they are seen is on the day of surgery. With discussion with the sponsor, it is felt that obtaining consent at REI, where the patients will be having their surgery, is most appropriate in terms of safety and it also allows potential participants to discuss elements of cataract surgery directly with the clinic team or the surgeons. If the consent is obtained at the study site, the academic researchers, who are not ophthalmologists, would not be able to discuss the surgical aspect related to this study. There is a long period between this pre-assessment appointment and the surgery (several weeks or months). So, the patients will have considerable time to further consider about their participation. At each study visit, time will be provided for participants to ask questions or reconsider their participation.

All potential participants will be informed that participation in this research study will be entirely voluntary. No one will be coerced against their will and no undue influence will be exerted upon the patient. The participants have the right to refuse participation without giving reasons and their decision will be respected. The participants are also free to withdraw at any time from the trial without giving

Vision and balance changes after bilateral implantation of Toric IOLs  
IRAS ID: 286913

reasons and without prejudicing his/her further treatment. Data collected up to the point of withdrawal from the study will be used in the analysis.

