### **7.3 The randomisation schemes**

The PI will be responsible for recruitment of potential participants from the Cataract clinic at UHP and oversee the consent and eligibility process carried out by the study coordinator. All potential participants will be allocated a unique identification number. The CI, who is independent of the outcome assessments and interventions, will randomize the participants between the intervention and control groups. He will allocate a pseudonymous participant number from 1 to 140. Using simple randomisation with 1:1 allocation ratio through random.org, the 1 to 140 number will be randomly assigned into two groups (Toric IOLs versus non-Toric IOLs). The randomization list will then be passed to the PI, who when recruiting the participants at the pre-surgery clinic can know which type of IOLs (Toric or non-Toric) to prepare for the cataract surgery. At study commencement, each number will be allocated to one of the two groups randomly. This means that subjects are allocated to either arm of the study at the point of recruitment. The randomized list will be held by the PI, who delivers the intervention surgeries. The PI needs to know which lenses are allocated to the patients for surgery purposes but will not participate in the outcome assessment. The study coordinator who is the assessor of the outcome measures will be masked to the allocation of lenses.

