### **10.3 Statistical analysis plan**

All data will be assessed for normality using a combination of assessing histogram plots and the Shapiro-Wilks Normality Test. Descriptive summary statistics for outcome measures relating to vision (acuity and refraction) will be recorded as mean +/- standard deviation.

Mixed ANOVA and post-hoc Bonferroni tests will be used to determine the statistical differences in the baseline characteristics and outcome measures between the Toric monofocal IOLs group and the non-Toric monofocal IOLs group. The between-subjects factor would be type of IOL lens and the within-subjects factor would be time (pre-surgery vs post-surgery). Level of significance will be set at 0.05.

Vision and balance changes after bilateral implantation of Toric IOLs  
IRAS ID: 286913

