#### **13.3 Public and Patient Involvement**

A Public and Patient Involvement (PPI) has been included at the protocol development stage. A total of seven participants were involved in the PPI to comment on the proposed study. A summary report can be found in appendix 16.4

This study follows on directly from previous research and is similar in structure to the clinical trials on IOLs conducted by the research team. We have evaluated the use of these lenses at UHP which demonstrated excellent visual outcomes following Toric implantation:

Vision and balance changes after bilateral implantation of Toric IOLs  
IRAS ID: 286913

With regards to similar randomised clinical trials, our experience comes from a very similar RCT with the same recruitment strategy and number of follow ups. The study has been published last year as shown in the reference below.

Cataract surgery is a positive experience. Regardless of the arm that the participant is randomised to, they will have good visual outcomes following removal of the cataract. Our previous experience of IOL RCTs have been that participants have a positive experience and that we have few dropouts.

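### Section 10.6 discards the data of randomised participants who silently miss a visit, section 7.2 keeps data up to withdrawal, and no readable section defines an as-randomised analysis set

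*Combined protocol and SAP*

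**What the plan says.** Section 10.6, headed for missing or spurious data, concerns a participant who misses a study visit without notification. Two more contact attempts are made within two months of the planned date, and a letter is sent. If four weeks pass without a reply, "they will be withdrawn from the study and any related data will be discarded". The section does not say which data count as related.

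Section 7.2 closes a paragraph on the right to withdraw with the sentence "Data collected up to the point of withdrawal from the study will be used in the analysis". Section 7.8 describes much the same failed contact and says only this about status: "Participants who are not contactable will be marked as lost to follow-up". It gives no rule for the data.

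On the timing of allocation, section 7.3 states that "subjects are allocated to either arm of the study at the point of recruitment". Section 10.5, on the participant population, restates eligibility and names no analysis set. Sections 6.2 (surgery other than traditional phacoemulsification) and 7.9 (eligibility reassessed) also allow removal after allocation, without a data rule.

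The planned analysis in 10.3, 10.3.2 and 10.3.3 is a mixed ANOVA. Section 10.3 gives time two levels, before and after surgery. Section 10.3.2 compares the lens groups "before surgery and 6 months after second eye surgery", but also lists three collection points. The flow diagrams cannot be read in the available text, so the statement that no analysis set is defined applies to the readable sections only.

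**The concern.** The same person can fall under two rules. Section 10.6 itself calls the silent non-responder withdrawn, and section 7.2 says what happens to the data of people who withdraw. Two analysts following this plan could build different data sets.

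Because lenses are allocated at recruitment, a missed study visit comes after randomisation. Excluding people for it gives up part of the protection that randomisation provides. If silent non-attendance differs between the lens groups, and non-attenders change differently from attenders, the comparison is biased.

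The rule is also not confined to the last visit. Someone who silently misses visit 2 is withdrawn, although the pre/post comparison needs only visits 1 and 3 and that person might have attended visit 3.

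**Working it through.** **1. The rules side by side.** Take a participant who attends visit 1, misses visit 2 without notice, and answers neither the two attempts nor the letter.
- Under 10.6, the participant is withdrawn and related data are discarded. A missed visit yields no data, so the natural reading is the visit 1 record. Visit 3 does not take place.
- Under 7.2, the participant is withdrawn (the term used in 10.6) and the visit 1 record is used.
- Under 7.8, the participant is lost to follow-up, with nothing said about data.

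**2. The plan's own sample size.** Inputs from 10.1: f = 0.25, alpha 0.05, power 85%. The documents give neither the number of measurements m nor the correlation; I assume m = 2 and correlation 0.5. For the between-group test in a repeated-measures ANOVA, the noncentrality is f² × N × m / (1 + (m − 1) × correlation).
- N = 110: 0.0625 × 110 × 2 / 1.5 = 9.17, power 0.851. This reproduces 55 per group.
- After 20% dropout: 140 × 0.8 = 112, power 0.857.

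**3. Participants removed from the pre/post contrast by 10.6.** Assume time has two levels (visit 1 and visit 3), total loss of 5–20% (7–28 of 140), a quarter to a half of it silent misses of visit 2, and a quarter to a half of those willing to attend visit 3.
- Low: 7 × 0.25 × 0.25 = 0.4 participants (0.3% of 140).
- High: 28 × 0.5 × 0.5 = 7 participants (5%).

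People who never attend visit 3 drop out of this ANOVA under either rule. If instead all three visits enter a complete-case ANOVA, anyone without visit 2 is dropped under either rule, and deleting the clause alone changes 0 participants.

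**4. Whether withdrawal can precede visit 3.** Section 8.6 says that "the second eye cataract surgery would be scheduled at around four months after the first eye surgery". The visit 3 window is therefore 4 + 3 = 7 to 4 + 6 = 10 months after first-eye surgery. Visit 2 is planned at month 3, 4, 5 or 6. Adding up to 2 months of attempts and 4 weeks for the letter (about 0.9 month) puts withdrawal by about month 5.9, 6.9, 7.9 or 8.9. For a visit 2 planned at month 3 or 4, withdrawal comes before the visit 3 window opens.

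**5. Bias attributable to 10.6.** Bias in the change contrast = (gap after − gap before) × difference in loss between arms. Assume non-responders are 0.3 SD worse at baseline and 0.3–0.5 SD worse afterwards. If all 7 participants from step 3 were in one arm of 70, the difference is 7/70 = 10 points.
- (0.3 − 0.3) × 0.10 = 0.
- (0.5 − 0.3) × 0.10 = 0.02 SD.

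**6. Visit records discarded (upper bounds).** Planned records: 140 × 3 = 420. If every planned dropout (28) is a silent non-responder after visit 1:
- all at visit 2: 28 × 1 = 28 records (6.7%);
- all at visit 3: 28 × 2 = 56 records (13.3%).

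At 5% loss the bounds are 7 to 14 records (1.7–3.3%). Voluntary withdrawals fall under 7.2 and lose none; a silent miss of visit 1 has no earlier study-visit record to lose.

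**7. What a model using partial visits would gain.** Assume three visits, SD 1, equal correlation r, and all loss at visit 3. The contrast is the lens difference in change from visit 1 to visit 3. With n per arm at visits 1 and 2 and c completers per arm:
- completers only: variance = 2 × 2(1 − r)/c;
- all observed visits: variance = 2 × [e/c + (2(1 − r) − e)/n], where e = 1 − 2r²/(1 + r).

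| Loss | c of n | r | SE, completers | SE, all visits | Variance reduction |
|---|---|---|---|---|---|
| 20% | 56 of 70 | 0.5 | 0.189 | 0.183 | 6.7% |
| 20% | 56 of 70 | 0.7 | 0.146 | 0.142 | 5.9% |
| 5% | 66.5 of 70 | 0.5 | 0.173 | 0.172 | 1.7% |
| 5% | 66.5 of 70 | 0.7 | 0.134 | 0.133 | 1.5% |

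**The case against.** The best defence is that 7.2 concerns voluntary withdrawal and 10.6 is a deliberate exception for people who cannot be reached. The position of the 7.2 sentence allows this. But that sentence is not limited to voluntary withdrawal, 10.6 uses the term withdrawn, and neither section states an exception. Section 7.8 is silent on data, so it does not contradict 10.6; it simply does not settle the matter.

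The trigger is also narrow: no notice, two further attempts and an unanswered letter. A participant who rings to rearrange is not affected. Section 13.3 reports from earlier lens trials that "participants have a positive experience and that we have few dropouts", and section 7.4 says participants learn their lens only at the end of the final visit. Both points make a large effect less likely, and both stand.

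A reader might infer that the records will be destroyed. The documents do not establish that: section 11.4 archives all original documents and data files for 10 years, so the clause may mean only exclusion from the analysis. That exclusion is enough for the point made here.

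Finally, the precision gain in step 7 belongs to the mixed model. Deleting the clause does not produce it while a complete-case ANOVA remains. That is correct, and the two changes should be judged separately.

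**Conclusion.** The point holds at modest size and should be fixed. The plan states a rule that excludes randomised participants on a post-randomisation event, a second section points the other way, and no readable section defines the analysis set.

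Three stronger readings are not supported:
- **The trial loses power.** It does not: 112 remain against 110 required.
- **The bias reaches 0.04 SD.** That needs a 20-point difference in loss between arms, (0.5 − 0.3) × 0.20. The 0 to 7 people whom 10.6 affects can produce at most about 10 points, hence about 0.02 SD. A wider gap would reflect ordinary attrition, which is present whichever section governs.
- **Up to 13% of records will be lost.** That is a ceiling, reached only if all 28 planned dropouts are silent non-responders at visit 3.

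The 0 to 7 count rests on a two-level time factor and three assumed proportions. The bias range rests on assumed gaps, and whether loss differs by lens is unknown. The precision gain of 1.5–1.7% at 5% loss, and up to 6–7% at 20% loss, rests on assumed correlations of 0.5–0.7 and on all loss falling at visit 3.

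**What to change.** 1. Delete the discard clause in 10.6 and align the section with 7.2 and 7.8. All data collected up to withdrawal or loss to follow-up are kept and used, and a missed visit 2 alone does not remove a participant from visit 3 or from the analysis.
2. State in 10.5 that the primary analysis set is all randomised participants in their allocated arm, and say how the exclusions in 6.2 and 7.9 relate to it.
3. In 10.3, 10.3.2 and 10.3.3, for the continuous outcomes, replace the complete-case mixed ANOVA with a likelihood-based linear mixed model on all observed visits, with visit-by-lens terms.

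The first two changes resolve the contradiction even if the third is not adopted, but participants without visit 3 would then stay out of the pre/post contrast. The cost is a few sentences in these sections, slightly more analysis work and no extra patients. Up to about 7 visit 3 attendances that would otherwise be lost may have to be held. The change should be made before 10.6 is first applied.
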